 It the data is coded, explain where the participants will be identified only collocked and separate from other reserver code (e.g. 12698afd) that and blood or tissue samples. Recollocked cabinet and will be destroyed (MULLING]]]Explain why, where, in research data/specimens into a report of the participant of the provided explains of the provided explanation of the provided explains of the provided explains of the provided explanation explanation of the provided explanation of the provided explanation of the provided explanation of the provided explanation explana	the key to identifiers will be stored, how it will be pro- on a signed consent form and initial screening form t search data. Each subject will be assigned a random t will be used to identify them in association with all rds identifying individuals will be kept in [name] of ad (shredded) following completion/publication of the what format, and for how long data/specimens will b ository for future use, please identify that here. Pleas DRIf you feel you will not be asked to submit data for ease specify your procedures for management of da s will be kept for a minimum of three (3) years after the kept in [name] office/laboratory in a locked cabin ess to the data. If required, data maybe released to g inch records. Specimens will be kept in a secure spate e HPCRL will have access to this space. estroyed at a specific date? How will this be destroyed is will be kept for a minimum of three (3) years after the ard (paper) copies will be shredded, and electronic to the ard (paper) copies will be shredded, and electronic to the ard (paper) copies will be shredded, and electronic to the strong of the space state to the space state to the ard (paper) copies will be shredded and electronic to the ard (paper) copies will be shredded and electronic to the state specific date? How shredded and electronic to the ard (paper) copies will be shredded and electronic to the state specific date? How shredded and electron	tected, and who will have access to it. hat will be kept hy generated 8- other research data fice/laboratory in a e project. be retained.If you intend to deposit your se outline any plans for submitting data for r open source or do not intend to archive your ata and destruction. the completion of the net. Only the governmental icce within the Human Performance Clinical ed? [definition: destruction of information the completion of the records containing identifying information

	0 -Protocol	PROTO IRB Fo	COL rm D	Protocol # 21-10634H ate Printed: 03/24/2021				
	Protocol Title:	Protocol Title: Interaction between Cannabidiol Meal Indestion, and Liver Function						
	Protocol Status:		APPROVED					
	Date Submitted:	03/03/2021	03/03/2021					
	Approval Period:	03/24/2021-03/17/2022	2					
	Important Note:	Important Note: This Print View may not reflect all comments and contingencies for approval. Please check the comments section of the online protocol. Questions that appear to not have been answered may not have been required for this submission. Please see the system application for more details.						
11 a & and sup	reconsenting materials. Info signed consent)Waiver of D (waiver of parental permissi exempt qualifying research) ConsentPlease label each it each document is aiming to b apply ONLY to Exempt application porting documentation in the Attact	rmed consent can be obta ocumentation (verbal, cov on or participant consent)/ Debriefing (post participati tem appropriately so your address. ons.NOTE: If you are completing chments section of the application	ined through varied proce er letter, 'Click to Consent Alteration (formal, signed o on providing addt'l informa IRB reviewers understand an Exempt application, please u n.	sses: Consent (formal, ' or implied consent)Waiver consent with deception or ation)Screening what purpose/population pload all your consent, recruitment				
a)	N/A							
b)	How will subjects be informed they	v will subjects be informed they may withdraw at any timewithout penalty?						
Note: A	Attach, in the Attachments Section,	written and/or verbal instructions	the subject will receive.					
See s	ample consent forms at htt	ps://www.research.colosta	te.edu/ricro/irb/templates/	1/				
Please	provide consent process backgrou	nd information below.	P					
	Informed Consent							
	Title	Consent Type	Attached Date	Submitted Date				
	Consent 21-10634H	Consent	03/19/2021					

* * * Assent Background * * *

12. Assent Background: What is assent? Assent is a process of soliciting affirmative acknowledgement from minors (or vulnerable populations who are unable to give adequate consent) to participate in your research. Assent can be obtained by various means appropriate to the population. Per 46.408(a), consider age, maturity, and psychological state of the children involved in your research as you develop an assent procedure. Even the IRB determines that the subjects are capable of assenting, the IRB may still waive the assent requirement under circumstances in which a consent may be waived (46.116).

(Complete if applicable)

03182021

Assent Procedure: Unlike the regulatory required elements of consent, assent elements are not defined by regulations. Assent is the affirmative acceptance to participate in research and should still be solicited in a population-specific manner. Assent can be a form or script of information that will be conveyed to the participant about the study. Assent language should be at a level understandable to the participant and be accompanied with adequate discussion. If the study includes a broad range of capacity to consent (whether age or cognition), more than one assent procedure may be needed (i.e., an assent form suitable for a 17 year old is not usually suitable for a 7 year old child).

Assent Waiver: In some cases, all or some of your participants may be incapable of providing affirmative assent to participate (based on age or diminished intellectual capacity). In such cases, the IRB may waive the requirement for assent.

See sample consent/assent forms at https://vpr.colostate.edu/ricro/irb/templates/

Upload your appropriate assent documentation below. If there is more than one assent process, please properly label and identify to minimize

confusion during IRB review.

* * * HIPAA * * *

13. Health Insurance Portability and Accountability Act (HIPAA)

If you are using PHI and this page is not active you must return to the General Checklist and check the box regarding the use of PHI in this research.

The HIPAA Privacy Rule establishes the right of an individual to authorize a covered entity, such as health plan, health care clearinghouse or health care provider, to use and disclose his/her Protected Health Information (PHI) for research purposes.

The Privacy Rule defines the elements of individual information that comprise PHI and establishes the conditions under which PHI may be used or disclosed by covered entities for research purposes. It also includes provisions to allow an individual's PHI to be disclosed or used in research without the person's authorization (i.e., IRB Waiver of HIPAA Requirement Authorization).

Is Your Research Covered by HIPAA's Privacy Rule?

Protected Health Information (PHI) is health information with one or more of the following identifiers. For more information see: http://privacyruleandresearch.nih.gov/clin_research.asp or consult HIPAA Privacy Rule for Research

Research which involves the use of de-identified data is exempt from HIPAA requirements. In order to be de-identified data. NONE of the subject identifiers listed below can be collected, used, reviewed, recoded, accessed or disclosed.

Please review the following list and indicate if any of the information will be collected from any medical records for the purpose of this research project.

- 1. Names
- 2. Social Security Numbers
- 3. Telephone Numbers
- 4. All geographic subdivisions smaller than a state, including street address, city, county, precinct, zip code, and their equivalent geocodes, except for the initial three digits of a zip code, if according to the current publicly available data from the Bureau of the Census;
 - i. The geographic unit formed by combining all zip codes with the same three initial digits contains more than 20,000 people; and
 - ii. The initial three digits of a zip code for all such geographic units containing 20,000 or fewer people is changed to 000.
- 5. All elements of dates (except year) for dates directly related to an individual, including birth date, admission date, discharge date, date of death; and all wages over 89 and all elements of dates (including year) indicative of such age, except that such ages and elements may be aggregated into a single category of age 90 or older.
- 6. Fax Numbers
- 7. Electronic Mail Addresses
- 8. Medical Record Numbers
 - You must attach a data collection sheet identifying the data points being collected from the MRN
- 9. Health Plan Beneficiary Numbers
- 10. Account Numbers
- 11. Certificate/License Numbers
- 12. Vehicle Identifiers and Serial Numbers, including License Plate Numbers
- 13. Device Identifiers and Serial Numbers
- 14. Web Universal Resource Locations (URLs)
- 15. Internet Protocol (IP) Address Numbers
- 16. Biometric Identifiers, including Finger and Voice Prints
- 17. Full Face Photographic Images and any Comparable Images
- 18. Any other unique identifying number, character, or code (note this does not mean the unique code assigned by the Investigator(s)

		0 -Protocol	PR IF	ROTOCOL RB Form		Protocol # 21-10634H Date Printed: 03/24/2021
		Protocol Title: Protocol Status: Date Submitted: Approval Period: Important Note:	Interaction betw APPROVED 03/03/2021 03/24/2021-03/ This Print View m Please check the Questions that ap for this submission	veen Cannabidiol, Mea 17/2022 hay not reflect all comme comments section of th opear to not have been a n. Please see the system	al Inges ents and e online inswered m applica	tion, and Liver Function contingencies for approval. protocol. d may not have been required ation for more details.
		to code the research data)				
			* * * Drugs a	Ind Devices * * *		
14.	Dru Se Pro Ch No	ugs and Devices: Please p ction. Please describe the btocol Procedures.If this se ecklist, and your study doe t Applicable in the required	ovide Investigato dosing amounts (ction is required o s NOT include FI fields.	r's Brochure or Packa minimum & maximum due to your selection o DA-regulated drugs or	ige Inse) and so of Clinic FDA-re	erts of Drugs in the Attachment chedule of all drugs in the alTrials.gov on the General egulated devices, please type:
	Dru	ugs				
	Na	ame	IND Nur	nber (if applicable)		Type of Research
	nc	one	N/A			IND-Exempt
	Dru	ugs				
	Na	ime*		none		
		D NUMBER (If applicable)		IN/A		
	• • •			•		
Label						
		•	* * Potential Co	onflict of Interest * *	*	
15.	Po	tential Conflict of Interest				
Confl https:	ict of //www	Interest and the definitions relate w.research.colostate.edu/ricro/coi	to the Conflict of Inte	erest Policy and the followir	ig questio	ons, please refer
Confl	ict of	Interest: Please check Yes or No	for each item below.			
a)	Ν	Does the research involve a drug Personnel?	, device, or biological	invented by you, an immed	diate fami	ly member or other Research
b)	N Is the research sponsored by an entity with which you, an immediate family member, or other Research Personnel have a paid consulting or advising relationship?			ner Research Personnel have a paid		
c)	Ν	Will you, members of your imme compensation if the research ge	diate family, or other F nerates a favorable ou	Research Personnel receive	e special o	compensation or increased
d)	Ν	N Will you, members of your immediate family, or other Research Personnel receive any money, gift or anything of monetary value above and beyond the actual costs of enrollment, conduct of the research, and reporting on the results, including, but not limited to, finders fees, referral fees, recruitment bonuses, and an enrollment bonus for reaching an accrual goal or similar types of payments?				ney, gift or anything of monetary value n the results, including, but not limited n accrual goal or similar types of
e)	Ν	Do you, members of your immed volunteer services) that might co research project?	iate family or other Renstitute a conflict of in	esearch Personnel have an terest or an appearance of	y other in conflict o	terests or relationships (including f interest in connection with the
						Page 2 [°]

of 25

		0 -Protocol	PROTOCOL IRB Form	Protocol # 21-10634H Date Printed: 03/24/2021
		Protocol Title: Protocol Status: Date Submitted: Approval Period: Important Note:	Interaction between Cannabidiol, Meal APPROVED 03/03/2021 03/24/2021-03/17/2022 This Print View may not reflect all comments Please check the comments section of the o Questions that appear to not have been ans for this submission. Please see the system a	Ingestion, and Liver Function s and contingencies for approval. online protocol. swered may not have been required application for more details.
		research project?		
f)	Ν	Will the payment you receive for time and tests) be inconsistent w	services provided during the conduct of the researce th fair market value for those services?	ch (e.g., investigator and Research Personnel
Signi	ficant	Financial Interest: Please check	es or No for each item below.	
g)	Ν	Will you, your immediate family n services (e.g., consulting fees, ho review committees, board membi during the previous 12 months or conducting the research, as spec	nembers or other Research Personnel receive salar onoraria, research design, management position, in ership seminars, lectures or teaching engagements are expected to exceed \$5,000 over the next 12 m ified in the research agreement.	ries, royalties and/or other payments for dependent contractor, service on advisory or when totaled together exceeded \$5,000 ionths)? This excludes reasonable costs of
h)	N	Do you, your immediate family m stock options that exceed \$5,000 organization? This does not inclu institutional investment fund over investment decisions.	embers, or other Research Personnel hold any own and/or that constitute more than a five percent (5% de any interests held solely by reason of investmer which the investigator and/or his or her immediate	nership interests including stocks, bonds, or 6) ownership interest in the sponsoring nt in a business by a mutual, pension or other family do not exercise day-to-day control of
Minin	nizing	Risks and Disclosure to Subjects		
i)	Y	Have you disclosed any actual, p to disclose all such conflicts to all	otential or perceived conflicts of interest in the cons research participants in the research consent form	sent form? Research Personnel are required
j)	Wh pot	at steps, if any, have you taken or ential or perceived conflicts of inte	will you take to manage the conflict of interest and rest arising out of this research?	minimize the risks associated with any actual,
	Th Fo	e CBD formulations under investig ods will not be involved with any c	ation will be manufactured by Caliper Foods. Calip f the data/sample analysis. This information has b	per Foods will sponsor the research. Caliper een disclosed in the Consent Form.
lf you conce	ı chec ərning	cked Yes to any statement (a-h, ex g the potential conflict of interest.	cept f) above, please identify the research team m	ember(s) below and provide details
By su You v plan i durat	ıbmiti vill up requii ion oʻ	ting this form, you are attesting tha odate this disclosure form when ne red by the Institutional Review Boa f the research.	t you have read the Client HRPP Policy on Conflict w or changes in conflict of interest arise, and that y rd (IRB) to manage, reduce, or eliminate any actua	t of Interest and agree to abide by its terms. You will comply with any conflict management al or potential conflict of interest for the
Link t	o CS	U's Conflict of Interest Policy: http:	s://vpr.colostate.edu/ricro/coi/.	
			* * * Attachments * * *	
16.	Att be co un	tachments: Attach all releva seen by a participant must mmunications, tools, instrur derstand what purpose/pop	nt documentation to your research in this be reviewed and approved by the IRB. T nents, etc.Please label each item approp ulation each document is aiming to addre	s section. Any documentation that will his includes multiple riately so your IRB reviewers ess.
Attac	h rele	evant documents here. These coul	d include:	
	-	Grant proposal for congruent	cy review. Please adequately reference in the Fund	ling section.
	-	Collaborating Investigator's I	RB approval and approved documents	
	-	Debriefing Script: Grant/Sub-	contract	
	-	HIPAA Authorization Form fr	om HIPAA-covered entity	

- Interview/Focus Group Questions
- Investigator's Brochure
- Letters of Agreement/Cooperation from organizations who will help with recruitment

PROTOCOL IRB Form

Protocol Title:Interaction between Cannabidiol, Meal Ingestion, and Liver FunctionProtocol Status:APPROVEDDate Submitted:03/03/2021Approval Period:03/24/2021-03/17/2022Important Note:This Print View may not reflect all comments and contingencies for approval.
Please check the comments section of the online protocol.
Questions that appear to not have been answered may not have been required
for this submission. Please see the system application for more details.

- Methodology section of associated Thesis or Dissertation project

- Questionnaires
- Radiation Control Office approval material
- Recruitment Material (e.g., flyers, email text, verbal scripts)
- Sponsor's Protocol; Surveys
- Other files associated with the protocol (you can upload most standard file formats: xls, pdf, jpg, tif, etc.)

Please be sure to attach all documents associated with your protocol. Failure to attach the files associated with the protocol may result in this protocol being returned to you for completion prior to being reviewed.

Students: Be sure to attach the Methods section of your thesis or dissertation proposal. If this protocol is associated with a grant proposal, please remember to attach your grant and reference in the funding section.

To update or revise any attachments, please delete the existing attachment and upload the Tracked Changes version and Clean revised document for review.

Document Type	Document Name	Attached Date	Submitted Date
Recruitment Material (e.g., flyers, email text, verbal scripts)	21-10634H email recruitment	03/03/2021	03/03/2021
Recruitment Material (e.g., flyers, email text, verbal scripts)	21-10634H Recruitment	03/03/2021	03/03/2021
Other, supplemental information	Comparison of Five CBD Preparations	03/03/2021	03/03/2021
Other, supplemental information	CBD Pharmacokinetics Anti-Inflammatory	03/03/2021	03/03/2021
Other, supplemental information	Phytocannabinoids NAFLD Treatment	03/03/2021	03/03/2021

03/18/2021	NEW FORM Comme Sent (Cvcle 1)	nts		
03/19/2021	NEW FORM Response	ses		
03/23/2021	NEW FORM Responses	ses		
03/24/2021	NEW FORM Comme Received (Cycle 2)	nts		
03/24/2021	NEW FORM Comme Received (Cycle 2)	nts		

Statistical Analysis Plan NCT04971837 04/01/2022

All data, unless otherwise stated, are presented as mean and standard deviation. Statistical analyses were performed using dedicated, commercially available software (SigmaStat for Windows 3.5, Systat Software, Inc., Chicago, IL, USA). Differences in pharmacokinetic parameters between CBD formulations for CBD, and the CBD metabolites were explored using one-way analysis of variance (ANOVA) with repeated measures. Tukey's tests were used to further examine the identified main effects. The thermic effect of food was examined using two-way ANOVA with repeated measures comparing energy expenditure across time for the two conditions (i.e., CBD and placebo); respiratory exchange ratio and circulating concentrations of glucose, insulin, and triglycerides were compared in the same way. The thermic effect of food was also examined by comparing the area under the curve (trapezoidal method). Circulating markers of liver and kidney function were compared across time and between CBD formulations using two-way ANOVA with repeated measures and post-hoc Tukey's tests when appropriate. Relations between circulating CBD concentrations and markers of liver and kidney function. The level of statistical significance was set at p < 0.05.

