ropo	* * Title (Please indicate if the pr Interaction between Cannabidiol, Me Desed Start Date: Summary Provide a brief summary of the scope reader. This summary should be no if for this section? According to a recent consumer pol (over 25% of the population) report - use of CBD has outpaced our under body. In the current proposed project, we i CBD products. The focus of this pro CBD; (2) we will examine the potent examine the influence of different for	* Summary, Purpose, Procedures * otocol title is different from the proposal al Ingestion, and Liver Function 04/16/2021 Proposed End Da e of work of this project, using non-technical terms more than 200 words.Did you know that your con- l, over 20 million Americans regularly use cannab trying CBD at least once within the previous 2 yea derived products, such as CBD, is highly prevaler rstanding of the associated potential risks and ber wish to continue our ongoing collaboration with C ject is three-fold: (1) we will compare the pharmar- ial two-way interaction between a meal and one f rmulations of CBD on markers of liver function.	I title) ate: 04/15/2022 as that would be understood by a non-scientific issent is a great tool to reference the information bidiol (CBD). Moreover, 64 million Americans ars. Since the passing of the 2018 Agriculture int across North America. The acceleration of the nefits, and the way it is processed within the Caliper Foods, a Colorado-based manufacturer or incokinetics of different formulations of ingestible formulation of ingestible CBD; and, (3) we will

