
е -Ркотосо	PROTOCOL IRB Form	Protocol # 21-10634H Date Printed: 03/24/2021
Protocol Title:	Interaction between Cannabidiol	, Meal Ingestion, and Liver Function
Protocol Status:	APPROVED	
Date Submitted:	03/03/2021	
Approval Period:	03/24/2021-03/17/2022	
Important Note:	This Print View may not reflect all co Please check the comments section Questions that appear to not have b for this submission. Please see the s	omments and contingencies for approval. of the online protocol. een answered may not have been required system application for more details.
consensus appears to be that lowers the time to attain peak	prior ingestion of a high-fat meal increases the m circulating concentration (Tmax).	naximal concentration of circulating CBD (Cmax) and
One purpose of the proposed	project is to study the influence of a standardized	I meal on the pharmacokinetics of a CBD formulation.
Little is known about the influe metabolic rate above resting r of weight gain or loss. Furthe health and predictive of future properties, including anti-infla postprandial metabolism, give of postprandial metabolism.	nce of ingested CBD on postprandial metabolism netabolism) is considered an important physiolog , the dynamics of circulating glucose and triglyce cardiometabolic disease risk. CBD has been pui nmatory and antioxidant actions. Either of these n that CBD potentially does both, it appears likely	n. The thermic effect of feeding (i.e. the increase in ical determinant of energy balance, and therefore als rides following a meal are reflective of metabolic rported to have a variety of beneficial physiological individual properties alone could favorably modify y that CBD might improve the physiological regulation
One purpose of the proposed	project is to determine the influence of CBD on p	ostprandial metabolism.

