The liver plays a critical regula relationship between the use high daily dosing of cannabine may have therapeutic potentic on liver function in healthy ad whether it is water or lipid solu	tory role in postprandial metabolism, and also wi of cannabinoids and liver health is unclear. While hids may be detrimental, more recent studies are I for the treatment of non-alcoholic fatty liver dise ults have not been well described, and may be inf ble).	th the physiological processing of cannabinoids. The e early studies implied that exposure of the liver to ver suggesting that some cannabinoids, including CBD, ease. The acute effects of low dose CBD (e.g. 30 mg) fluenced by the formulation of the CBD product (i.e.
One purpose of the proposed liver function.	project is to determine the acute influence of diffe	erent formulations of CBD on circulating markers of
What do the investigators hope	to learn from this project?	
We hope to learn a little more CBD and a meal may interact CBD), and if low-dose CBD (3	about how the formulation of CBD influences the (i.e. how does CBD influence the digestion of a n 0 mg) influences liver function.	speed in which it is processed within the body, how neal, and how does a meal influence the processing of
Please describe your plans to designs.	share the results of this study with intentions to in	fluence behavior, practice, theory, future research
The results of the study will be In light of the prevalence of C information about CBD. Note publication, the abstract has b 2021).	submitted for publication in peer-reviewed scien 3D use in the USA, we hope the study will provide worthy, our previous CBD study (IRB Protocol 19- een viewed 1,307 times, and the full manuscript a	tific journals, and presented at scientific conferences. e users and manufacturers with useful physiological -9577H) was published on January 6th, 2021. Since accessed 970 times (articles metrics as of March 2,
Procedures		
Describe in chronological orde interventions/interactions with Please provide details of all re-	• of event(s) how the activities will be conducted, subjects, data collection, photographing, audio an search activities that a participant will be involved	providing information about all procedures (e.g. nd video recording), including follow up procedures.

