OVERVIEW Adult men and women will be (50 kg), body mass index grea use of any Cannabis or canna experimental procedures in 15	invited to participate. Inclusion criteria will include iter than 25 kg/m ² , absence of any gastrointestin bis containing products for three days prior to eac adults.	e: age over 18 years, body mass greater than 110 Lbs nal or metabolic diseases, and ability to refrain from ch laboratory visit. The goal is to complete all
Following screening (i.e. med participants will report to the la morning having abstained from instrumented for measurement kept patent via a saline drip.	cal history, and assessment of body composition b on seven separate occasions separated by a n n food for 12-hours, and any products containing t of heart rate and blood pressure. A venous cath	via dual energy X-ray absorptiometry (DEXA)) ninimum of 4-days. Participants will arrive in the CBD for 72-hours. On arrival participants will be heter will be introduced to an arm or hand vein and
Two of the visits will begin wit 30 mg dose of CBD or a place circulating markers of carbohy analysis of blood for circulatin	n measurement of resting metabolic rate followed bo. Postprandial metabolism will be studied usin drate and fat metabolism. Blood will also be sam o markers of liver function	l immediately by ingestion of a liquid meal and a singl ng indirect calorimetry and repeated blood sampling fo npled for determination of CBD pharmacokinetics and

The other five visits will comprise ingestion of different CBD formulations without a meal. Venous blood will be sampled at

C -PROTOCOL	PROTOCOL IRB Form	Protocol # 21-10634H Date Printed: 03/24/2021
Protocol Title: Protocol Status:	Interaction between Cannabidiol, Meal APPROVED	Ingestion, and Liver Function
Date Submitted:	03/03/2021	
Approval Period:	03/24/2021-03/17/2022	
Important Note:	This Print View may not reflect all comment Please check the comments section of the Questions that appear to not have been an for this submission. Please see the system	ts and contingencies for approval. online protocol. swered may not have been required application for more details.
standardized intervals over 4-hours a	and will be analyzed for circulating CBD concentra	tion and markers of liver function.
DETAILS		

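### The SAP's only pharmacokinetic comparison is between formulations, so the stated purpose of measuring a meal's effect on CBD pharmacokinetics has no named fed/fasted analysis

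*Combined protocol and SAP*

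**What the plan says.** The protocol states the purpose three times. The Summary describes a two-way interaction between a meal and one formulation. The Purpose section sets out to study the influence of a standardized "meal on the pharmacokinetics of a CBD formulation". The section on what the investigators hope to learn asks how CBD affects digestion of a meal "and how does a meal influence the processing of" CBD.

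The design collects the data. T-P-S-10 at 30 mg CBD is the first of the five products listed under the visits without a test meal. It is also the active product at the two test-meal visits, where the alternative is placebo. Both sections give the same CBD blood-sampling times: 0, 10, 20, 30, 45, 60, 120, 180 and 240 minutes. The Overview sets a goal of 15 adults completing all procedures.

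The SAP has one pharmacokinetic sentence: "Differences in pharmacokinetic parameters between CBD formulations for CBD, and the CBD metabolites were explored", by one-way repeated-measures ANOVA, followed by Tukey tests. Its only two-condition comparison is "comparing energy expenditure across time for the two conditions (i.e., CBD and placebo"). Respiratory exchange ratio, glucose, insulin and triglycerides are handled the same way. The document is headed "Statistical Analysis Plan NCT04971837 04/01/2022" and is written in the past tense.

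**The concern.** The interaction between CBD and a meal is in the trial's title, and it runs in two directions. CBD's effect on the response to the meal has a named analysis, CBD against placebo. The meal's effect on CBD has none. The CBD/placebo comparison cannot supply it, because no CBD is given at the placebo visit.

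If the analysis is left unnamed, three courses all fit the SAP text or are compatible with it: no fed/fasted test, one Tukey pair among many, or a dedicated paired test. These can lead to different conclusions from the same data, and a reader of the results could not tell whether the choice was made before or after the data were seen.

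**Working it through.** **Does the SAP wording cover the fed visit?** The protocol lists five formulations. The Overview reserves the phrase for the visits without a meal: "The other five visits will comprise ingestion of different CBD formulations without a meal". Fed T-P-S-10 repeats a product already on that list, so on its face a comparison between formulations has five levels and does not include it. The SAP does not list the ANOVA levels, so a sixth level cannot be ruled out. These two readings are taken in turn.

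- Five levels: 5×4/2 = 10 pairs, none of them fed against fasted. The purpose is not tested.
- Six levels: 6×5/2 = 15 pairs, one of them fed against fasted T-P-S-10.

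**What does the second reading cost?** The documents give no power calculation, effect size or within-person variability, so there is no stated figure to reproduce. Inputs:

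- n = 15 (protocol, Overview)
- two-sided 0.05 (the SAP gives p < 0.05; two-sided is assumed)
- within-person CV of 30%, 50% or 70% (assumed)
- a true fed/fasted ratio of 1.5 (assumed)

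Formulas, on the log scale: SDw = √ln(1+CV²); SE of the fed−fasted difference = SDw×√(2/15); noncentrality = ln(1.5)/SE, with ln(1.5) = 0.405. Power comes from the noncentral t distribution.

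Critical values:

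- Paired test, 14 df: t = 2.145.
- Unadjusted contrast in the six-level model, 5×14 = 70 df: t = 1.994.
- Tukey with six levels, 70 df: studentized range 4.144/√2 = 2.930.

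| Assumed CV | SDw | SE | Noncentrality | Power, Tukey pair | Power, paired test | Power, unadjusted in six-level model |
|---|---|---|---|---|---|---|
| 30% | 0.294 | 0.107 | 3.78 | 80% | 94% | 96% |
| 50% | 0.472 | 0.172 | 2.35 | 29% | 59% | 64% |
| 70% | 0.631 | 0.231 | 1.76 | 13% | 37% | 41% |

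The last column shows that the loss comes from the Tukey adjustment, not from adding a sixth level.

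**What would a named paired comparison deliver?** The 95% confidence limits are the estimated ratio multiplied and divided by exp(2.145×SE), which is 1.26, 1.45 and 1.64 at the three CVs. The smallest ratio detectable with 80% power is 1.38, 1.68 and 2.00. At the higher CVs a non-significant result would be weak evidence of no meal effect, so the interval matters more than the p-value.

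**The case against.** The strongest reply is that the SAP does not list the ANOVA levels. The fed visit may have been one, in which case the meal effect was tested and what remains is wording and multiplicity. That stands as a possibility, and the power figures for the Tukey pair apply only under it. It does not remove the gap: no sentence names the comparison, and under that reading it competes with 14 other pairs. A reader might go further and infer that the meal effect was never analysed. The documents show only that no analysis is named.

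A second reply concerns the fed-visit clock. A reader might infer that sampling was timed from the meal, so that recorded Tmax runs late and works against an expected shortening. The documents do not support this, for two reasons.

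- The section on the test-meal visits starts calorimetry immediately after the meal and CBD. Its eight 30-minute blocks fill 0–240 minutes, the same span as the blood schedule. This points to a clock that starts after CBD, although the protocol does not say so for blood.
- The expectation of a higher Cmax and shorter Tmax in the Purpose section concerns a high-fat meal. The test drink is listed at 5% of daily value for fat, and no direction is stated for it.

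Third, the lack of a planned confidence interval is not particular to this comparison. The SAP reports means, standard deviations and p-values throughout.

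Fourth, an unadjusted contrast within a six-level model would have slightly more power than the paired test. That is true under a common error variance across all six conditions. The paired test avoids that assumption at a small cost. Either would be acceptable if named.

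**Conclusion.** The concern holds for the missing comparison. A stated purpose, for which paired data are scheduled, is not served by the SAP's only pharmacokinetic analysis. Either the fed/fasted comparison is not made, or it is an unstated one of 15 Tukey pairs. In the second case, for an assumed 1.5-fold effect with n = 15, power falls from 94/59/37% to 80/29/13% at assumed CVs of 30/50/70%. The direction of that loss does not depend on the assumed CV or ratio; its size does.

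The timing of the fed-visit samples needs only a clarification, and it supports no claim of bias. This is a change that should be made. It does not put the design or the collected data in question.

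**What to change.** Amend the SAP in three places.

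1. State that the formulation ANOVA and its Tukey tests use the five visits without a meal.
2. Add one separate within-participant fed/fasted comparison for T-P-S-10, outside the Tukey family. Report the ratios of Cmax and AUC0-240 from a paired log-scale analysis with 95% confidence intervals, and a paired comparison of Tmax.
3. Add one line stating that blood-sample times run from CBD ingestion at both visits, if that is how they were recorded.

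Because the SAP is dated 04/01/2022 and reports analyses as already done, call the comparison prespecified only if results had not been seen by that date. Otherwise label it post hoc.

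The cost is wording and a short re-analysis of samples the protocol already schedules. The downside is three parameters compared without multiplicity adjustment. If the sponsor prefers Bonferroni over the three, the critical t becomes 2.718 (0.05/3 each, 14 df), and power for the same assumed 1.5-fold ratio falls to 84/39/21%.
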